6.0 STUDY POPULATION

The study population for this clinical trial consists of male and female adults who have been diagnosed with stage 2 resistant hypertension, on at least three (3) anti-hypertensive medications of which one is a diuretic. All potential study participants must meet all of the following eligibility criteria to qualify for enrollment in the study.

6.1 INCLUSION CRITERIA

Candidates for this study must meet the following criteria to be enrolled in the study, as determined in the following screening and baseline visits:

Baseline Screening Visit 1 – (Day 0 – 14) – Assessed on Day 14

1. Provided written informed consent;
2. ≥ 18 years of age and ≤ 80 years of age;
3. Office cuff SBP ≥ 160 mmHg measured per protocol instructions (Appendix VI) following at least one (1) month of maximally tolerated therapy with at least three (3) anti-hypertensive medications, of which at least one (1) must be a diuretic. Any combination medications will be counted per the active ingredient (for example, Zestoretic (Lisinopril +HCTZ) equals two (2) anti-hypertensive medications);
4. Renal artery imaging performed within the last 12 months showing no evidence of renal artery stenosis. Acceptable imaging modalities include renal duplex, magnetic resonance angiography, CT angiography, and selective or nonselective renal angiography depending on investigator site diagnostic standards. In the absence of adequate imaging testing this inclusion criteria could also be met by obtaining a renal duplex prior to enrollment or by performing nonselective renal angiography at the time of device implantation.
5. Compliant with medications (self-reported) and daily blood pressure readings – Subject must be a minimum 80% compliant with diary entries; and
6. For females (with child-bearing potential), a negative pregnancy test and the use of a medically accepted method of birth control for the duration of the trial.

Baseline Screening Visit 2 – (Day 15 – 30) - Assessed on Day 30

1. No significant obstructive vascular disease on CTA or MRA of the aortic arch and great vessels;
2. Carotid duplex studies demonstrating no obstructive carotid disease;
3. Continued adherence to hypertension medications without anticipated changes and daily blood pressure readings – Subject must be a minimum 80% compliant with diary entries;
4. Continued office cuff SBP ≥ 160 mmHg despite at least one (1) month of therapy at maximally tolerated therapy with at least three (3) anti-hypertensive medications, of which at least one (1) must be a diuretic. Any combination medications will be counted per the active ingredient (for example, Zestoretic (Lisinopril +HCTZ) equals two (2) anti-hypertensive medications).

Day of Procedure -

1. Continued adherence to hypertension medications without anticipated changes and daily blood pressure readings – Subject must be a minimum 80% compliant with diary entries.

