INCLUSION CRITERIA	
Baseline Screening Visit 1 – (Day 0 – 14) – Assessed on Day 14
 
1. Provided written informed consent;2. ≥ 18 years of age and ≤ 80 years of age;3. Office cuff SBP ≥ 160 mmHg measured per protocol instructions (Appendix IV) following at least one (1) month of maximally tolerated therapy with at least three (3) anti-hypertensive medications, of which at least one (1) must be a diuretic. Any combination medications will be counted per the active ingredient. (For example, Zestoretic (Lisinopril +HCTZ) equals two (2) anti-hypertensive medications);4. Renal artery imaging performed within the last 12 months showing no evidence of renal artery stenosis. Acceptable imaging modalities include renal duplex, magnetic resonance angiography, CT angiography, and selective or nonselective renal angiography depending on trial site diagnostic standards. In the absence of adequate imaging testing this inclusion criteria could also be met by obtaining a renal duplex prior to enrollment, or by performing nonselective renal angiography at the time of device implantation.5. Compliant with medications (self-reported) and daily blood pressure readings – Subject must be minimum 80% complaint with diary entries; and6. For females (with child-bearing potential), a negative pregnancy test, and the use of a medically accepted method of birth control for the duration of the trial. 
Baseline Screening Visit 2 – (Day 15 – 30) - Assessed on Day 30
 
1. No significant obstructive vascular disease or plaque on CTA or MRA of the aortic arch and great vessels;2. Carotid duplex studies demonstrating no obstructive carotid disease or plaque;3. Continued adherence to hypertension medications without anticipated changes and daily blood pressure readings – Subject must be a minimum 80% compliant with diary entries; and4. Continued office cuff SBP ≥ 160 mmHg despite at least one (1) month of maximally tolerated therapy with at least three (3) anti-hypertensive medications, of which at least one (1) must be a diuretic. Any combination medications will be counted per the active ingredient. (For example, Zestoretic (Lisinopril+HCTZ) equals two (2) anti-hypertensive medications). 
Day of Procedure -
 
1. Continued adherence to hypertension medications without anticipated changes and daily blood pressure readings – Subject must be a minimum 80% compliant with diary entries.

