
EXCLUSION CRITERIA	Baseline Screening Visit 1 – (Day 0 – 14) – Assessed on Day 14 
1. Known or clinically suspected baroreflex failure or autonomic neuropathy;2. Hypertension secondary to an identifiable and treatable cause other than sleep apnea (e.g., hyperaldosteronism, renal artery stenosis, pheochromocytoma, Cushing's disease, coarctation of the aorta, hyperparathyroidism and intracranial tumor);3. Treatable cause of resistant hypertension including, but not limited to, improper BP measurement, volume overload and pseudotolerance (excessive sodium intake, volume retention from kidney disease, inadequate diuretic therapy), drug-induced or other causes (non-adherence, inadequate doses, inappropriate combinations, NSAIDs, COX-2 inhibitors, cocaine, amphetamines, or other drugs, sympathomimetics, oral contraceptives (confirmed cause of resistant hypertension), adrenal steroids, cyclosporine, and tacrolimus, erythropoietin, licorice (including some chewing tobacco), ephedra, ma haung, bitter orange); and excessive alcohol intake;4. Arm circumference greater than 46cm and/or BMI \geq 40;5. Chronic atrial fibrillation or recurrent atrial fibrillation with episode within the last 12 months;6. Vulnerable plaque or ulceration of any size in the carotid artery or aortic arch;7. History of bleeding complications with dual anti-platelet therapy in the past or has known uncorrectable bleeding diathesis;8. Current use of additional anticoagulation therapy. Examples include vitamin K antagonists like warfarin, direct thrombin inhibitors, direct factor Xa inhibitors, thrombin IIa inhibitors like apixaban, rivaroxaban, dabigatran and etexilate;9. Peptic ulcer disease with documented active ulcer or bleeding within the last year.10. History of allergy to contrast dye that cannot be managed medically;11. History of orthostatic hypotension;12. History of syncope within the last six (6) months;13. History of myocardial infarction or unstable angina within the past three (3) months;14. History of cerebral vascular accident (stroke or TIA) within the past year;15. Severe chronic kidney disease (calculated GFR < 45 ml/min);16. Prior surgery, radiation, or endovascular stent placement in either

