17. Clinically significant structural valvular cardiac disease;
18. Moderate to severe reactive airway disease, chronic obstructive pulmonary disease, or primary pulmonary hypertension;
19. Uncompensated congestive heart failure or known severe reduction in left ventricular function (EF < 30%);
20. Uncontrolled co-morbid medical condition that would adversely affect participation in the trial;
21. Non-controlled diabetes mellitus;
22. Active infection within the last month;
23. Co-morbid condition that reduces life expectancy to less than one (1) year;
24. Mental health issues that would prohibit the subject's availability to meet the Protocol requirements;
25. Currently taking an imidazoline receptor agonist or central sympathetic treatment;
26. Enrolled in a concurrent clinical trial;
27. Unable or unwilling to fulfill the protocol follow-up requirements;
28. Subject is a prisoner or member of other protected population;
29. Planned surgery or other procedure within the next six (6) months;
30. Deep venous thrombosis (DVT) within the last year or documented recurrent DVT.

[figure not shown]
[figure not shown]
Baseline Screening Visit 2 – (Day 15 – 30) - Assessed on Day 30

1. ICA lumen diameters < 5 mm or > 11.75 mm within the planned location of the device placement via CTA or MRA;
2. Carotid hypersensitivity detected by carotid massage or typical history, as described in the Protocol (Appendix V); or
3. Significant aortoiliac or common femoral artery disease that will prohibit safe femoral access.

Day of Procedure – Angiographic

1. Evidence of plaque, ulceration or any stenosis on selective carotid angiography performed in orthogonal views. Lumen diameters will be assessed to exclude subjects with ICA lumen diameters smaller than 5 mm or larger than 11.75 mm within the planned location of the device placement;
2. Any angiographic evidence of plaque or ulceration in the aortic arch and/or the supra aortic vasculature;

	

3. Inappropriate anatomy of the carotid bifurcation for deployment of the MobiusHD, including, but not limited to, tortuosity of the extracranial vessels and significant angulation of the common carotid artery bifurcation; or
4. Type III arch or horizontal takeoff of the left carotid from the innominate and any calcification of the carotid bulb.

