6.2 EXCLUSION CRITERIA

Candidates will be ineligible for enrollment in the study if any of the following conditions are identified at the screening or baseline visits:

Baseline Screening Visit 1 – (Day 0 – 14) – Assessed on Day 14

1. Known or clinically suspected baroreflex failure or autonomic neuropathy;
2. Hypertension secondary to an identifiable and treatable cause other than sleep apnea (e.g., hyperaldosteronism, renal artery stenosis, pheochromocytoma, Cushing's disease, coarctation of the aorta, hyperparathyroidism and intracranial tumor);
3. Treatable cause of resistant hypertension including, but not limited to, improper BP measurement, volume overload and pseudotolerance (excessive sodium intake, volume retention from kidney disease, inadequate diuretic therapy), drug-induced or other causes (non-adherence, inadequate doses, inappropriate combinations, NSAIDs, COX-2 inhibitors, cocaine, amphetamines, or other drugs, sympathomimetics, oral contraceptives (confirmed cause of resistant hypertension), adrenal steroids, cyclosporine, and tacrolimus, erythropoietin, licorice (including some chewing tobacco), ephedra, ma haung, bitter orange); and excessive alcohol intake;
4. Arm circumference greater than 46 cm and/or BMI \geq 40;
5. Chronic atrial fibrillation;
6. Vulnerable plaque or ulceration of any size in the carotid artery or aortic arch;
7. History of bleeding complications with dual anti-platelet therapy in the past or has known uncorrectable bleeding diathesis;
8. Current use of additional anticoagulation therapy. Examples include vitamin K antagonists like warfarin, direct thrombin inhibitors, direct factor Xa inhibitors, thrombin IIa inhibitors like apixaban, rivaroxaban, dabigatran and etexilate;
9. Peptic ulcer disease with documented active ulcer or bleeding within the last year;
10. History of allergy to contrast dye that cannot be managed medically;
11. History of orthostatic hypotension;
12. History of syncope within the last six (6) months;
13. History of myocardial infarction or unstable angina within the past three (3) months;
14. History of cerebral vascular accident (stroke or TIA) within the past year;
15. Severe chronic kidney disease (calculated GFR < 45 ml/min);
16. Prior surgery, radiation, or endovascular stent placement in either carotid region;

17. Clinically significant structural valvular cardiac disease;

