18. Moderate to severe reactive airway disease, chronic obstructive pulmonary disease, or primary pulmonary hypertension;
19. Uncompensated congestive heart failure or known severe reduction in left ventricular function (EF < 30%);
20. Uncontrolled co-morbid medical condition that would adversely affect participation in the trial;
21. Non-controlled diabetes mellitus;
22. Active infection within the last month;
23. Co-morbid condition that reduces life expectancy to less than one (1) year;
24. Mental health issues that would prohibit the subject's ability to meet the protocol requirements;
25. Currently taking an imidazoline receptor agonist or receiving central sympathetic treatment;
26. Enrolled in a concurrent clinical trial;
27. Unable or unwilling to fulfill the protocol follow-up requirements;
28. Subject is a prisoner or member of other protected population;
29. Planned surgery or other procedure within the next six (6) months; or
30. Deep venous thrombosis (DVT) within the last year or documented recurrent DVT.

Baseline Screening Visit 2 – (Day 15 – 30) - Assessed on Day 30

1. ICA lumen diameters < 5 mm or > 11.75 mm within the planned location of the device placement via CTA or MRA;
2. Carotid hypersensitivity detected by carotid massage or typical history, as described in the study protocol; and
3. Significant aortoiliac or common femoral artery disease that will prohibit safe femoral access.

Day of Procedure – Angiographic

1. Evidence of plaque, ulceration or any stenosis by angiographic evaluation in orthogonal views of the carotid artery. Lumen diameters will be assessed to exclude subjects with ICA lumen diameters smaller than 5 mm or larger than 11.75 mm within the planned location of the device placement;
2. Any plaque or ulceration on the arch angiogram involving the aortic arch and/or the origin of the great vessels;
3. Inappropriate anatomy of the carotid bifurcation for deployment of the MobiusHD, including, but not limited to, tortuosity of the extracranial vessels and significant angulation of the common carotid artery bifurcation; and

4. Type III arch or horizontal takeoff of the left carotid from the innominate and calcification of the carotid bulb.

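### The synopsis and Section 6 give different current eligibility lists: 4 of 48 criteria can change who may be implanted, and Section 6.1 cites the wrong appendix for blood pressure measurement

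*Combined protocol and SAP*

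**What the plan says.** Sections 1.0 and 6.1–6.2 of the combined protocol and SAP each set out the complete eligibility list, with the same numbering. Both are current text; neither is a record of changes.

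- **Visit 2, CTA/MRA (inclusion 1).** Synopsis: "No significant obstructive vascular disease or plaque on CTA or MRA of the aortic arch and great vessels". Section 6.1: "No significant obstructive vascular disease on CTA or MRA of the aortic arch and great vessels".
- **Visit 2, carotid duplex (inclusion 2).** Synopsis: "Carotid duplex studies demonstrating no obstructive carotid disease or plaque". Section 6.1: "Carotid duplex studies demonstrating no obstructive carotid disease", with no mention of plaque.
- **Visit 1, exclusion 5.** Synopsis: "Chronic atrial fibrillation or recurrent atrial fibrillation with episode within the last 12 months". Section 6.2: "5. Chronic atrial fibrillation", and nothing further.
- **Day of procedure, exclusion 2.** Synopsis: "Any angiographic evidence of plaque or ulceration in the aortic arch and/or the supra aortic vasculature". Section 6.2: "Any plaque or ulceration on the arch angiogram involving the aortic arch and/or the origin of the great vessels".

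For the qualifying office systolic pressure (Visit 1 inclusion 3), the synopsis cites Appendix IV and Section 6.1 cites Appendix VI. The appendix list shows that IV holds the blood pressure instructions and VI the Instructions for Use. Sections 8.5–8.7 cite Appendix IV.

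Section 6.0 requires every criterion in its own list to be met but does not say that this list overrides the synopsis. Sections 8.7–8.9 refer to the inclusion and exclusion criteria without saying which list is meant.

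**The concern.** This is a first-in-man study of a carotid implant. Its primary outcome is the incidence of SAEs and UADEs from implantation to six months, so the set of people who may be implanted defines the population for that outcome. With two lists in force, that set is not defined once.

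The practical consequence is an unlabelled difference between subjects. A site working from Section 6 could implant someone the synopsis excludes, be fully compliant with the text it followed, and have nothing to report under Sections 16.4 and 19.0. A site working from the synopsis would screen-fail the same person. Section 7.0 then asks for a screening-log entry but no CRF, although Section 8.4 asks for CRFs on everyone who consents.

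The trial plans 20 subjects at two to ten sites, in two cohorts of 10. One subject is therefore 1/10 = 10% of a cohort and 1/20 = 5% of the trial.

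**Working it through.** The plan states no figure on this point, so the check is a criterion-by-criterion comparison.

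**Size of each list**

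- Inclusion (Visit 1 + Visit 2 + procedure day): 6 + 4 + 1 = 11
- Exclusion (Visit 1 + Visit 2 + procedure day): 30 + 3 + 4 = 37
- Total: 11 + 37 = 48 in each list

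**Wording comparison, ignoring case, punctuation and spacing**

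| Type of difference | Criteria | Count |
|---|---|---|
| Can change eligibility | Visit 2 inclusions 1 and 2; Visit 1 exclusion 5; procedure-day exclusion 2 | 4 |
| Appendix reference | Visit 1 inclusion 3 (IV against VI); Visit 2 exclusion 2 (Appendix V in the synopsis, none in 6.2) | 2 |
| Minor wording | Visit 1 inclusions 4 and 5; Visit 2 inclusion 4; Visit 1 exclusions 24 and 25; procedure-day exclusions 1 and 4 | 7 |
| List connector only | Visit 2 inclusion 3; Visit 1 exclusion 29; procedure-day exclusion 3 | 3 |
| **All differences** | 4 + 2 + 7 + 3 | **16** |
| No difference | 48 − 16 | **32** |

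Share that can change eligibility: 4/48 = 8.3%. The connector differences have no effect, because Section 6.2 makes a candidate ineligible if any one condition is present. The closest borderline item is Visit 1 exclusion 24 (availability against ability). Counting it would give 5 of 48 and leave the finding unchanged.

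**What other Section 6 criteria already catch**

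- *Plaque at Visit 2.* Section 6.2 separately excludes vulnerable plaque or ulceration in the carotid artery or arch. On the procedure day it excludes carotid plaque on angiography and plaque on the arch angiogram in the arch or great-vessel origins. What remains is mainly non-obstructive plaque outside the protocol's definition of vulnerable plaque, seen on CTA/MRA or duplex but not on procedure-day angiography. In the unilateral cohort the gap may be wider: Section 8.9 calls for selective angiography of the target vessel, whereas the duplex criterion is not limited to one side. That depends on the imaging guidelines (Appendix I), whose text is not in the document.
- *Recurrent atrial fibrillation.* The partial checks are current anticoagulant use, stroke or TIA within a year, uncontrolled co-morbidity, and the Visit 1 history and ECG. A subject with a recent episode who takes no anticoagulant and has had no stroke or TIA can pass all of them. None makes recurrent atrial fibrillation an exclusion.
- *Arch angiogram.* What remains is supra-aortic plaque beyond the vessel origins that the carotid angiography criterion does not catch. This is narrow.

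**The case against.** The strongest reply is that the gap rarely matters by the time of implantation, which is when the primary outcome starts to count. Under Section 6 alone, plaque seen at angiography in the arch, the great-vessel origins or the examined carotid still bars implantation. This stands, and it makes both the CTA/MRA difference and the arch-angiogram difference small in practice. It does not reach recurrent atrial fibrillation, or plaque that angiography does not show.

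The synopsis wording on CTA/MRA can also be read as no *significant* plaque, and its population statement speaks of significant arch and great-vessel disease. That reading is possible. It still differs from Section 6.1, which does not mention plaque at that step.

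Section 13.0 promises a profile of all CRF fields and a narrative for each subject, and the DSMB adjudicates every SAE and UADE. A discordant subject might therefore be spotted by hand. That is fair for a study of this size, but a reader would first need to know which list to check against.

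The Inclusion/Exclusion iCRF may already impose one list at every site. The sample CRFs (Appendix III) are not in the available text, so differing use across sites is a possibility rather than an established fact. Finally, 8.3% counts criteria; it does not measure risk. The blood pressure citation is also likely to be corrected in use, since Sections 8.5–8.7 point to Appendix IV.

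**Conclusion.** The concern holds. Two current eligibility lists conflict on four criteria that can change who receives the implant, with Section 6 looser each time, and no passage ranks one list above the other. The clearest difference is recurrent atrial fibrillation, followed by the two Visit 2 plaque criteria; the arch-angiogram difference is narrow. The Appendix VI citation in Section 6.1 is a plain error against the protocol's own appendix list.

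The effect is on the definition of the population. No sample size, endpoint or other stated figure changes. The documents give no rate of discordant enrolment, so no effect on SAE incidence can be computed and no bias is claimed. The 4-of-48 count rests on treating the remaining 12 differences (2 + 7 + 3) as not affecting eligibility. This should be corrected, but it does not undermine the descriptive analysis plan.

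**What to change.** 1. Reconcile Sections 1.0 and 6.1–6.2 line by line into one identical list, covering the four criteria above and the appendix references for blood pressure measurement and carotid massage. The clinical team decides the clinical wording; this review takes no position on which version is right.
2. State that this list governs, and build the Inclusion/Exclusion iCRF from it.
3. In Section 6.0, refer to Section 16.4, which allows a sponsor-approved prospective deviation when a single criterion is unmet. That route is consistent with Section 19.0 and only the cross-reference is missing. Whether to keep it is the sponsor's choice.
4. Optionally, mark in the safety listings any subject enrolled with an unmet criterion.

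The cost is amendment wording, plus the optional mark in the listings. Sample size, visits and assessments do not change.

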6.2 EXCLUSION CRITERIA

Candidates will be ineligible for enrollment in the study if any of the following conditions are identified at the screening or baseline visits:

Baseline Screening Visit 1 – (Day 0 – 14) – Assessed on Day 14

1. Known or clinically suspected baroreflex failure or autonomic neuropathy;
2. Hypertension secondary to an identifiable and treatable cause other than sleep apnea (e.g., hyperaldosteronism, renal artery stenosis, pheochromocytoma, Cushing's disease, coarctation of the aorta, hyperparathyroidism and intracranial tumor);
3. Treatable cause of resistant hypertension including, but not limited to, improper BP measurement, volume overload and pseudotolerance (excessive sodium intake, volume retention from kidney disease, inadequate diuretic therapy), drug-induced or other causes (non-adherence, inadequate doses, inappropriate combinations, NSAIDs, COX-2 inhibitors, cocaine, amphetamines, or other drugs, sympathomimetics, oral contraceptives (confirmed cause of resistant hypertension), adrenal steroids, cyclosporine, and tacrolimus, erythropoietin, licorice (including some chewing tobacco), ephedra, ma haung, bitter orange); and excessive alcohol intake;
4. Arm circumference greater than 46 cm and/or BMI \geq 40;
5. Chronic atrial fibrillation;
6. Vulnerable plaque or ulceration of any size in the carotid artery or aortic arch;
7. History of bleeding complications with dual anti-platelet therapy in the past or has known uncorrectable bleeding diathesis;
8. Current use of additional anticoagulation therapy. Examples include vitamin K antagonists like warfarin, direct thrombin inhibitors, direct factor Xa inhibitors, thrombin IIa inhibitors like apixaban, rivaroxaban, dabigatran and etexilate;
9. Peptic ulcer disease with documented active ulcer or bleeding within the last year;
10. History of allergy to contrast dye that cannot be managed medically;
11. History of orthostatic hypotension;
12. History of syncope within the last six (6) months;
13. History of myocardial infarction or unstable angina within the past three (3) months;
14. History of cerebral vascular accident (stroke or TIA) within the past year;
15. Severe chronic kidney disease (calculated GFR < 45 ml/min);
16. Prior surgery, radiation, or endovascular stent placement in either carotid region;

17. Clinically significant structural valvular cardiac disease;
18. Moderate to severe reactive airway disease, chronic obstructive pulmonary disease, or primary pulmonary hypertension;
19. Uncompensated congestive heart failure or known severe reduction in left ventricular function (EF < 30%);
20. Uncontrolled co-morbid medical condition that would adversely affect participation in the trial;
21. Non-controlled diabetes mellitus;
22. Active infection within the last month;
23. Co-morbid condition that reduces life expectancy to less than one (1) year;
24. Mental health issues that would prohibit the subject's ability to meet the protocol requirements;
25. Currently taking an imidazoline receptor agonist or receiving central sympathetic treatment;
26. Enrolled in a concurrent clinical trial;
27. Unable or unwilling to fulfill the protocol follow-up requirements;
28. Subject is a prisoner or member of other protected population;
29. Planned surgery or other procedure within the next six (6) months; or
30. Deep venous thrombosis (DVT) within the last year or documented recurrent DVT.

Baseline Screening Visit 2 – (Day 15 – 30) - Assessed on Day 30

1. ICA lumen diameters < 5 mm or > 11.75 mm within the planned location of the device placement via CTA or MRA;
2. Carotid hypersensitivity detected by carotid massage or typical history, as described in the study protocol; and
3. Significant aortoiliac or common femoral artery disease that will prohibit safe femoral access.

Day of Procedure – Angiographic

1. Evidence of plaque, ulceration or any stenosis by angiographic evaluation in orthogonal views of the carotid artery. Lumen diameters will be assessed to exclude subjects with ICA lumen diameters smaller than 5 mm or larger than 11.75 mm within the planned location of the device placement;
2. Any plaque or ulceration on the arch angiogram involving the aortic arch and/or the origin of the great vessels;
3. Inappropriate anatomy of the carotid bifurcation for deployment of the MobiusHD, including, but not limited to, tortuosity of the extracranial vessels and significant angulation of the common carotid artery bifurcation; and

4. Type III arch or horizontal takeoff of the left carotid from the innominate and calcification of the carotid bulb.

